- a) Clinical de-identified data will be collected on the quality of stem cell mobilization. Examples of data being collected but not limited to will include the following: number of patients undergoing stem cell mobilization, demographics, cycles received prior to stem cell mobilization, CD34 blood counts prior to collection, total stem cell yield, mobilization failure rates, and subsequent attempts of mobilization

Assessment/Evaluation Plan

The protocol consent form asks participants for permission for re-contact to discuss research findings if an incidental research finding is made that may be critical to their health or preventive care, or that of their issue. If a participant agrees to be re-contacted, he/she will not be told the specific results of the research test, but will be informed that his/her samples were used in a project and a potential risk was discovered. If the participant is interested in further discussion of the research findings, he/she will be asked to contact MSKCC Clinical Genetics Service for counseling and specific genetic testing.

The below schema will be followed by MSKCC investigators who identify a potentially actionable incidental finding in the course of research conducted on samples collected under this protocol:

In the event an investigator's research identifies a finding that he or she believes should be communicated to the subject (and/or family designee), the investigator shall communicate this to the OCR-IRB. The finding will be reviewed by a group convened by the IRB to determine whether the incidental finding should be discussed with the subject. In the event that group determines that the finding should be discussed with the subject, and the subject has consented to be re-contacted, then the treating/consenting physician shall be contacted by the OCR-IRB representative and asked to refer the subject to the Clinical Genetics Service for further discussion of the research finding. After appropriate counseling and consent, the Clinical Genetics Service will request permission to confirm the result in a New York DOH-approved laboratory prior to communication of the specific result. If the patient is not available (e.g. deceased), then the surrogate designated on the consent will be contacted and the above will occur.

The IRB and Clinical Genetics Service, as per above flow chart, will be notified when a participant's samples uncover a potentially reportable incidental finding(s). The following information must be provided to OCR-IRB representative and Clinical Genetics:

- Participant Name/MRN #
- Type of Biospecimen (tissue, blood, etc)
- Incidental Finding
- Project # (Waiver or Biospecimen Protocol #) that this analysis occurred under
- Collection Protocol #

Contact: [contact]

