In the past decade, multiple myeloma patients have reached deeper response rates with use of effective anti-myeloma therapeutics, immunomodulatory agents and proteasome inhibitors, approximating up to 75% patients achieving near-complete response (>90% decrease in monoclonal protein) or complete response (100% decrease in monoclonal protein). In general, improved therapeutics and deeper response rates have resulted in improved overall survival of multiple myeloma patients across most age groups. As a result, there has been an increasing demand for the development of sensitive assays to detect minimal residual disease (MRD) in treated MM patients. In MM patients receiving autologous stem cell transplant, MRD-negative status using multi-parametric flow cytometry (MFC) is associated with improved progression free survival and overall survival. Similar studies using next generation sequencing methods for MRD have also been shown to be associated with improved outcomes in MM MRD-negative patients. In our prior study, among the 25 patients with CR/sCR that were assessed by MFC for immunophenotypic abnormal plasma cells; 25 out of 25 were negative for (MRD with an overall MRD negative rate of 25/43 (58)% (*2 patients did not have evaluable samples) using MFC. Using next generation sequencing molecular tests, the CR/sCR MRD negative rate was 13/33 (39%) (*12 patients did not have evaluable samples) (Sequentia platform). In patients with NDMM treated with CRd, 12-month progression-free survival for MRD-negative vs MRD-positive status by flow cytometry and next-generation sequencing was 100% vs 79% (95% CI, 47%-94%; $P < .001$) and 100% vs 95% (95% CI, 75%-99%; $P = .02$), respectively.

Minimal Residual Disease Platforms

A recent survey including 30 major institutions in the US found major heterogeneity in MRD testing of multiple myeloma by flow cytometry²². In brief, there was considerable variation in the number of bone marrow cells analyzed (events) and number of abnormal plasma cells needed to define the presence of MRD, which affects maximum possible sensitivity. The maximum detection sensitivity ranged from 0.0005% to 0.02%, a 100-fold difference in sensitivity. Also, the variation in antibodies studied and definition of an abnormal plasma cell by flow cytometry affected the ability to differentiate normal from neoplastic plasma cells.

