Subjects who are positive for Anti-HBc or Anti-HBs will undergo testing for hepatitis B DNA by PCR. Subjects with serologic findings suggestive of HBV vaccination (Anti-HBs positivity as the only serologic marker) and a known history of prior HBV vaccination do not need to be tested for HBV DNA by PCR. During and following study treatment, subjects who have history of HBV infection will be closely monitored for clinical and laboratory signs of reactivation of HBV as specified in the Time and Events Schedule (Section 10.0). Where required by local law, the results of HBV testing may be reported to the local health authorities.

Research and clinical laboratory tests to be performed within 4 weeks of study entry and prior to starting therapy

- Bone Marrow
 - Histopathological evaluation on bone marrow aspirate and biopsy
 - Immunophenotyping of aberrant clonal plasma cells by multiparametric flow cytometry.
 - Immunoglobulin heavy and/or light chain rearrangement.
 - Interphase FISH/cytogenetics
 - To create a bone marrow and peripheral blood sample bank of whole BM lysate, CD 138+ fractions and CD 138- fractions cell sorting with subsequent correlatives on both fractions. These samples may be used to later evaluate

biological activity of carfilzomib, lenalidomide, and dexamethasone. Potential analyses include sequencing and gene expression profiling on pre and post therapy bone marrow samples, identification of potential biomarkers (blood, urine, bone marrow aspirates), and evaluation of proteasome activity.

- Sample for NGS MRD should be bone marrow aspirate (not biopsy and not CD138 purified, per the assay validation) 1mL, frozen at -70°C.
- Patients who have completed 1 cycle of SOC therapy who meet eligibility criteria and have an HOTB sample at MSK within 60 days of cycle 1 day 1, will not need an additional bone marrow biopsy or aspirate, unless clinically indicated.
- Peripheral Blood/Urine
 - Peripheral blood and urine samples for storage and establishing a biobank.
 - Immune cells – including, but not limited to T cells (CD4 and CD8), LGL, and NK cells.
 - Indirect Coombs Test or other tests required by the local blood bank needed before treatment with CD38-antibodies.

Imaging (FDG/PET/CT scan) within 8 weeks of study entry and prior to starting therapy

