Flow cytometry: Immunophenotyping of aberrant plasma cells by flow cytometry currently involves, but is not limited to, the use of the following reagents: CD138, CD19, CD45, CD38, and CD56.

Characteristic changes in immunophenotypically abnormal plasma cells (CD38 bright and/or CD138 positive) include but are not limited to decreased or absent CD19 and CD45, decreased CD38, increased CD56, decreased CD27, decreased CD81, increased CD117. For patients with non-evaluable samples at MRD assessment, patients can opt for repeat MRD assessment or continue to receive a total of 8 cycles of CRd. The first pulled bone marrow sample will be sent for multi-parametric flow cytometry as a priority. Samples will undergo MRD testing per MSK institutional practice, see section 12.0 for further methodology practice.

Molecular pathology: For MRD samples utilizing the NGS LymphoSIGHT™ (Adaptive, CA) platform, the InVivoScript NGS platform, immunoglobulin heavy and kappa chain variable, diversity, and joining gene segments from genomic DNA obtained from CD138+ bone marrow (BM) cell lysate or cell-free supernatant BM aspirate were amplified using universal primer sets as described elsewhere²¹. An MM clonotype was defined as an immunoglobulin rearrangement identified by NGS.

Mass spectrometry based proteomics for minimal residual disease assessment: Serial urine and serum samples will be analyzed to detect clonotypic peptides representing patient's monoclonal immunoglobulin heavy and light chains using high resolution mass-spectrometry-based proteomics.

FISH and cytogenetics

Interphase FISH/cytogenetics will be performed on patients enrolled in this protocol.

DNA-based target mutations

Bone marrow aspirate samples will be analyzed for somatic mutations by exome-sequencing of targeted genes using MSK *myTYPE* platform (or equivalent e.g. MSK Impact Heme). After therapy, perform if response is \leq PR or evidence of gross residual disease on SPEP/UPEP

Cell Sorting and Bone marrow cell lysate

Bone marrow aspirate storage samples will be sorted into CD 138 + and CD 138 – fractions and whole bone marrow cell lysate per HOTB SOP.

Research Blood/Serum and Urine

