The study includes safety suspension rules; throughout the study we will monitor for grade 3 or higher heart failure. These safety suspension rules will be applied separately in the two cohorts. In the event that the rule is crossed (see Table below), the study will be suspended for that cohort and all safety data will be reviewed by the PI. We will report all SAEs per standard guidelines (Section 17.2). In addition, throughout the study we will monitor for grade 4 or higher adverse events related to study drugs; if the PI notices there is a safety signal, the study will be suspended and all safety data will be reviewed by the PI.

Failure Type	# of failures needed to suspend the study	Failure rate in the population	Probability boundary is crossed
Heart failure/Ischemic heart disease (grade 3 or higher) Or grade 4 or higher adverse events due to study drug.	3 in the first 17 patients 4 in the first 29 patients 5 patients at any point	0.05	0.1
		0.2	0.95

The above numbers apply for each of the cohorts. Each cohort will be assessed independently.

Secondary Objective. Objectives 1, 2, and 3 below will be evaluated separately for the two cohorts.

1. To evaluate the safety and tolerability of the combination therapy. Toxicities will be summarized by grade and cycle of therapy. Patients who receive any study drug will be included in this assessment.
2. To evaluate the rates of best overall response (partial response (PR) or better), very good partial response (VGPR) or better, and complete response (CR) or stringent CR (sCR) for the evaluable patients. See section 12.0 for response definitions. Response proportions along with exact 95% confidence intervals will be reported.
3. Kaplan-Meier methods will be used to estimate overall and progression-free survival. . Patients who receive any study drug will be included in this assessment.
4. To compare MRD techniques of multi-parametric flow cytometry with 1) next-generation sequencing and 2) mass spectrometry using summary statistics. Rates of concordance for the measures will be estimated. This will be evaluated among all MRD assessments.

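### The NGS MRD specimen is specified in two conflicting ways, and the pooled flow-versus-NGS concordance rate has no direction and counts patients unequally

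*Combined protocol and SAP*

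**What the plan says.** Section 8.0, under the baseline marrow tests, gives a handling instruction: "Sample for NGS MRD should be bone marrow aspirate (not biopsy and not CD138 purified, per the assay validation) 1mL".

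Section 10.0, molecular pathology, describes the NGS MRD method as working on "genomic DNA obtained from CD138+ bone marrow (BM) cell lysate or cell-free supernatant BM aspirate". It opens with "For MRD samples utilizing the NGS LymphoSIGHT™ (Adaptive, CA) platform, the InVivoScript NGS platform", so two platforms are named, with no rule for which applies or whether results are combined. Flow has first call on the marrow: "The first pulled bone marrow sample will be sent for multi-parametric flow cytometry as a priority". The pull used for NGS is not stated. The marrow time-point table in the same section stores both sorted material and whole lysate at every time point.

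Section 12.0 defines MRD by a validated method with sensitivity expressed per nucleated cell, and reserves the primary endpoint for flow cytometry. Section 3.0 gives the reason for the comparison: no data exist on the sensitivity of the in-house flow assay relative to molecular assays.

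Section 14.0, secondary objective 4, compares flow with 1) "next-generation sequencing and 2) mass spectrometry using summary statistics", and adds: "Rates of concordance for the measures will be estimated. This will be evaluated among all MRD assessments". It gives no rule for repeated assessments, time point, baseline pairs or non-evaluable pairs. The by-cohort rule covers objectives 1 to 3 only.

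**The concern.** There are two separate problems.

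The first is the specimen. Section 8.0 says the assay validation excludes CD138-purified material, yet the text describing NGS for MRD samples uses it. A CD138+ fraction, or cell-free DNA, does not share the nucleated-cell denominator of flow on whole marrow. Discordance caused by the material could then be reported as a difference between assays.

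The second is the summary measure. The stated purpose is to learn how the assays compare in sensitivity. A raw concordance rate does not say which assay found disease that the other missed. Computed over all assessments, it also gives more weight to patients with more marrows, and the number of marrows is not fixed by design.

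**Working it through.** Objective 4 states no sample size, expected concordance or precision, so there is no figure of the plan's own to reproduce on this point.

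**1. Specimen texts side by side.**
- Section 8.0: 1 mL aspirate, unsorted, validation cited, but placed among pretreatment tests.
- Section 10.0, first option: CD138+ lysate. This is what Section 8.0 rules out.
- Section 10.0, second option: cell-free supernatant. It is not CD138-purified, so it does not breach that clause, but it is not the aspirate sample described.
- Later MRD time points: no other section settles which applies, and both sorted and whole material are in storage.

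**2. Why the denominator matters.** Let a clone be a fraction f of nucleated cells and plasma cells a fraction p. In a pure CD138+ sort that keeps the whole clone, the clone is f/p of the cells. A cut-off set per nucleated cell therefore means something else unless the result is converted back. The documents give neither p nor a reporting rule, so no size can be attached.

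**3. Direction.** Among n pairs, let a = both positive, b = flow negative and NGS positive, c = flow positive and NGS negative, d = both negative.
- Concordance = (a + d)/n.
- Difference in detection, NGS minus flow = (b − c)/n.
- If concordance is 80% (assumed), b + c = 20% of pairs. The difference can then be anywhere from −20 points (b = 0) to +20 points (c = 0).

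**4. Unequal weighting.** The marrow schedule in Section 10.0 comprises CR/sCR, end of therapy, and years 1, 2 and 3, so up to five post-baseline marrows. The yearly ones are optional and as per standard of care. Footnote h leaves the end-of-study marrow to standard of care once MRD negativity is confirmed earlier. The number of marrows thus depends partly on the MRD result. Assume half the patients have concordance 0.90 and half 0.60, so the patient average is 75.0%.
- The 0.90 half gives one assessment, the 0.60 half gives three: (0.5×0.90×1 + 0.5×0.60×3)/(0.5×1 + 0.5×3) = 1.35/2 = 67.5%.
- The reverse: (0.5×0.90×3 + 0.5×0.60×1)/2 = 1.65/2 = 82.5%.

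**5. Baseline pairs.** Flow and rearrangement testing are also done at baseline. If 82 baseline pairs, all concordant positives, were counted with 82 post-treatment pairs at 70%: (82×0.70 + 82)/164 = 85%. All inputs except the maximum of 82 patients (Section 4.1) are assumptions.

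**6. Precision, if an interval is reported.** With 82 pairs and concordance 0.80, the 95% half-width is 1.96×√(0.80×0.20/82) = 8.7 points (9.9 at 0.70, 6.5 at 0.90). With three assessments per patient, the interval that ignores clustering is 1.96×√(0.16/246) = 5.0 points. Multiplying by √(1 + 2×ICC) gives 6.3, 7.1 or 8.1 points at an assumed ICC of 0.3, 0.5 or 0.8.

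**The case against.** The best defence is that the Section 10.0 wording is carried-over method text. It is in the past tense, refers to a description elsewhere, and sits under a list of potential studies on stored samples. Section 8.0 is the only explicit handling instruction, and if it is followed at every time point a paired concordance can be read. That stands. It explains the conflict but does not remove it, because Section 8.0 speaks of baseline and Section 10.0 of MRD samples. A reader might infer that the comparison is bound to be uninterpretable; the documents support only that it may be.

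The objective is also descriptive, with no interval, test or power planned, and summary statistics could include a 2x2 table. That stands too. Clustering matters only if an interval is given, so a fixed inflation of the variance should not be read into the plan.

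Three further inferences fail:
- Section 3.0 reports the prior study's flow results "among the 25 patients with CR/sCR that were assessed by MFC", all negative, and an NGS-negative rate of 13/33. A reader might conclude that concordance in CR patients will equal 39%. But 33 exceeds 25, so the NGS rate cannot come from those patients alone. This trial also assesses MRD in VGPR patients and uses a different flow assay.
- A reader might infer that pooling over-weights patients who stay negative. Footnote h could equally give them fewer marrows.
- A reader might assume 1% plasma cells and claim a 100-fold shift (1/0.01) for sorted material. The plan gives no plasma-cell fraction and does not say whether sorted results are converted back.

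**Conclusion.** The concern holds in limited form. The specimen conflict is real and unresolved, and its effect depends on which material is used; no size can be derived from the documents. The concordance measure cannot answer the sensitivity question in Section 3.0 whatever specimen is used. Its weighting can move the estimate by 7.5 points either way in the example, on assumed concordance values and marrow counts, with the direction unknown. Counting baseline pairs could raise it by 15 points, again on assumed inputs.

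A reader might infer that the primary result is at risk. It is not: Section 12.0 uses flow alone for that endpoint. The Simon design (28 then 41 patients, thresholds 12 and 21) has exact error 0.0951 at 40% and power 0.9009 at 60%, within its stated 0.10 limits. This is a secondary objective that should be repaired, not a threat to the trial's main conclusion.

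**What to change.** **Sections 8.0 and 10.0.** Reconcile the two texts so that one validated specimen type and one named NGS platform apply at all MRD time points. Report any NGS result from sorted or cell-free material separately from the main concordance analysis.

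**Section 14.0, objective 4.**
- Main analysis: one post-baseline flow/NGS pair per patient, chosen by a rule that does not depend on the flow result, for example the first on-treatment MRD assessment with both assays evaluable. A rule based on the end-of-therapy marrow would depend on it, because footnote h relaxes that marrow for patients already MRD negative.
- Report the 2x2 table, positive agreement 2a/(2a + b + c), negative agreement 2d/(2d + b + c), and the discordant proportions b/n and c/n with exact intervals.
- Exclude baseline pairs.
- Show all-assessment concordance as supportive, with patient-clustered intervals.

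The cost is wording in three sections and the loss of a few sorted or repeat samples from the main secondary analysis. No extra marrow is needed.

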11.0 TOXICITIES/SIDE EFFECTS

Carfilzomib

Likely Side Effects: those occurring in more than 20% or more than 20 out of 100 persons who receive carfilzomib:

- Fatigue (tiredness)
- Fever
- Headache
- Cough

- Shortness of breath (at rest or with exertion) which in rare cases may be life-threatening or resulting in death
- Nausea
- Vomiting
- Diarrhea
- Constipation
- Decreased red blood cell count which may lead to feeling tired
- Decreased platelet counts which may lead to increase bleeding or bruising
- Decreased white blood cell count which may decrease your ability to fight infection
- Upper respiratory tract infection
- Mild decreases in kidney function which are generally reversible
- Swelling of arms or legs
- Back pain
- Inflammation of the liver (mild, reversible changes in liver function tests)

Less Likely Side Effects: those occurring in 5-20% or 5 to 20 out of 100 persons who receive carfilzomib:

- Flu-like symptoms such as fever, chills, or shaking that may occur at any time but are more likely to occur on the day of or the day after carfilzomib infusion
- Decreased or worsening of heart function including chest pain, abnormal heart rhythm, heart attack, and heart failure. This can be serious, potentially life threatening event.
- Loss of/or decreased appetite which may lead to weight loss
- Insomnia (difficulty sleeping)
- Dizziness
- High blood pressure
- Abnormal physical weakness or lack of energy
- Blurred or double vision
- Numbness, tingling, painful or decreased sensation in hands and/or feet
- Blood chemistry and electrolyte alterations
- Rash and/or itching, or dry skin
- Pneumonia
- Pain, burning or irritation at the infusion site
- Generalized pain
- Pain in the bones or joint pain or extremities
- Muscle spasm, pain, weakness

Rare and/or Potentially Serious Side Effects: these have occurred in less than 5% or in less than 5 out of 100 persons who receive carfilzomib:

- Herpes zoster reactivation
- Liver failure
- Acute kidney failure
- Increase in the blood pressure in the arteries of the lungs (Pulmonary Hypertension)
- Infusion reactions (which can occur during or shortly after carfilzomib infusion) including flushing or feeling hot, fever, shakes, nausea, vomiting, weakness, tightness in the chest,

and low blood pressure , shortness of breath, swelling of the face, pain in the muscles or joints, tightness or pain in the chest, and low blood pressure

- Allergic reaction including total body rash, hives, and difficulty breathing
- Tumor Lysis Syndrome: Caused by rapid killing of tumor cells during dosing. When the tumor cells die, they release their contents into the bloodstream. If cell killing is very rapid, this can affect blood chemistries and the kidneys. In severe cases, this can lead to shutdown of kidney function requiring dialysis
- Posterior reversible encephalopathy syndrome (PRES): A rare condition that causes swelling of the brain and affects how it functions. A person with PRES may experience headaches, confusion, loss or decreased level of consciousness, blurred vision or blindness, seizures, and possibly death. If caught early and treated, PRES may be reversed.

